Overall, EDP-305 was generally safe, with the majority of TEAEs being mild to moderate. The most common ( $\geq 5\%$ ) TEAEs with EDP-305 included pruritus, rash, gastro-intestinal (GI) related symptoms (nausea, vomiting, diarrhea), urinary tract infection, dizziness, decreased appetite and cough. As for tolerability of EDP-305 in this 12-week phase 2a study, pruritus was present in approximately 51% of the subjects in the 2.5 mg arm compared to less than 10% in the 1 mg arm and less than 5% in the placebo arm, with the majority being mild or moderate in severity. Among subjects with severe pruritus, there were 2 subjects in the 2.5 mg arm and 2 subjects in the 1 mg arm compared to none in the placebo arm. There were no study discontinuations due to severe pruritus except for one subject in the 1 mg arm. Overall, the incidence of treatment discontinuation due to pruritus was 1.8% for 1 mg and 20.8% for 2.5 mg and none in the placebo arm, with all the discontinuations in the 2.5 mg arm being due to moderate pruritus.

Based on Common Terminology Criteria for Adverse Events (CTCAE) grading, there were very few treatment-emergent laboratory abnormalities in the EDP-305 arms: Grade 3 increase in serum/plasma glucose were observed more frequently in subjects taking EDP-305 with 7% in the 1 mg arm, 21% in the 2.5 mg arm, and 4% in the placebo arm. Likewise, grade 3 uric acid increase were observed more frequently in subjects taking EDP-305 with 18% in 1 mg, 19% in 2.5 mg and 4% in placebo. In addition, one subject with a Grade 3 amylase, and one subject with a Grade 3 ALT were reported in the 2.5 mg arm.

There were no clinically significant changes in ECG or vital signs, and no other clinically significant laboratory abnormalities.

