## 11. STATISTICAL CONSIDERATIONS

### 11.1. General Considerations

Statistical analysis of this study will be the responsibility of Enanta Pharmaceuticals or its designee. Details of the statistical analysis methods will be described in the statistical analysis plan (SAP) document.

Continuous endpoints will be summarized using n, mean, standard deviation, median, 25th quartile, 75th quartile, minimum and maximum values. Categorical endpoints will be summarized by the number of subjects meeting the endpoint and the percentage of subjects out of the appropriate population. The denominator will be displayed when needed. Statistical inference will be performed as appropriate. Inferential testing will be conducted using a 2-sided alpha of 0.05, unless stated otherwise.

Any change to the data analysis methods described in the protocol will require an amendment if it changes a principal feature of the protocol. Any other change to the data analysis methods described in the protocol, and the justification for making the change, will be described in the clinical study report or SAP. Changes may only be made in the SAP prior to unblinding.

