#### **11.6.1. Secondary Efficacy Analysis**

Secondary endpoints will be analyzed for treatment group differences. Multiple sensitivity analyses will be performed on the primary efficacy endpoints.

For categorical endpoints (e.g., proportions) a logistic regression model testing between treatment differences with terms for diabetes status and use of Vitamin E and/or pioglitazone and baseline covariate NAS included in the model. Odds ratio and the 95% confidence intervals will be reported. If convergence is encountered the Fisher's exact test will be used to test treatment group differences.

For continuous endpoints (e.g., change from baseline) an analysis of covariance (ANCOVA) model testing treatment differences with terms for baseline diabetes status and use of Vitamin E and/or pioglitazone, baseline covariate NAS, and baseline parameter of interest included in the model. A type III sum-of-squares for the least-squares means and 95% confidence intervals will be reported.

When continuous endpoints that are repeated over visits a restricted maximum likelihood-based mixed model repeated measures (MMRM) technique may be performed. The model will include treatment, baseline covariate NAS, baseline parameter, visit, treatment-by-visit interaction as fixed effects. An unstructured variance-covariance structure will be considered to model the within-patient error. If the unstructured covariance matrix results in a lack of convergence, the heterogeneous Toeplitz covariance structure should be used. The Kenward-Roger method will be used to estimate the denominator degrees of freedom. A type III sum-of-squares for the least-squares means and 95% confidence intervals will be reported.

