#### **Mixed Model Repeated Measures (MMRM) analysis**

A MMRM analysis will be performed for secondary efficacy endpoints that are continuous in nature and assessed over multiple study visits. The SAS procedure PROC MIXED will be used. The preferred model will include the fixed categorical effects of treatment group, visit, treatment-by-visit interaction as well as the continuous fixed covariates of baseline measurement for the parameter of interest and baseline NAS score. An unstructured variance-covariance structure will be considered to model the within-patient error. If the unstructured covariance matrix results in a lack of convergence, the heterogeneous Toeplitz covariance structure should be used. The Kenward-Roger method will be used to estimate the denominator degrees of freedom. A sample of SAS code for MMRM is provided in [Appendix A](#).

The model will provide least-squares means (using type III sum-of-squares), standard errors, p-value and 2-sided 95% confidence interval for treatment differences for each visit.

[figure not shown]

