#### **8.6.3.2.1 Change from baseline in 5D-itch scale and Visual Analog Score (VAS) through week 72**

Pruritus will be monitored in this study at day 1, 7, weeks 2, 4, 8, 12, 16, 20, 24, 28, 32, 36, 40, 44, 48, 56, 64, 72 and EOS.

Observed values, change from baseline, and percentage change from baseline for VAS scores and each dimension of 5D-itch scale and overall score will be summarized using an 8-number summary by visit and treatment group.

Change from baseline for VAS and 5D-itch scale will be analyzed using a restricted maximum likelihood-based mixed model repeated measures (MMRM) technique. The model will include treatment, visit, treatment-by-visit interaction as fixed effects along with baseline NAS score and baseline score for VAS and 5D-itch scale as covariate respectively. Variance-covariance structure to be used to model the within-patient error and results to be presented are described in [Section 8.6.1](#). The details for calculation of score is given in [Appendix B](#).

A by-subject listing will be provided for observed and derived variables for VAS and 5D-itch scale.

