## Final Analysis Statistical Analysis Plan (SAP)

### 9 CHANGES TO PLANNED ANALYSIS FROM STUDY PROTOCOL

This study was terminated by Enanta on October 4th, 2021. At the time the study was terminated no subject had completed Week 72 study assessments. Any analyses planned through week 72 will present all data collected through study termination, and only summary statistics will be provided post Week 12 visit. Any analyses at week 72 will not be performed.

Consequently, the following analyses will not be performed,

SAP Section	Analysis: Endpoint(s)
8.6.2	Primary Efficacy: All
8.2.6.1	Sensitivity Analyses for Primary Endpoints: All
8.6.3.1	Secondary Efficacy Analysis: Categorical Endpoints (Responder at Week 72) – All
8.6.2.3.4	Secondary Efficacy Analysis: Continuous Endpoint Adiponectin through week 72
8.6.4.2	Exploratory Analysis at Week 72: NAFLD Fibrosis Score, AST to Platelet Ratio Index
8.6.4.3	Exploratory Analysis at Week 72: CRP, IL-6, IL-1 $\beta$ , TNF- $\alpha$ , TNF- $\beta$ , alpha2 macroglobulin and haptoglobin levels
8.6.4.5	Exploratory Analysis: ASCVD Score
8.8	Pharmacokinetics (PK) and Pharmacokinetics/Pharmacodynamics (PK/PD) Analysis: All Analyses with the following exceptions: 
 
• Summary of AUC0-8 and AUC2-8 for C4, change from baseline and percentage change from baseline at Week 12 for subjects with and without pruritus
 
• Scatterplot of FGF19 concentrations at Week 12 vs FGF19 Week 12 Change from Baseline value
 
• Scatterplot of C4 concentrations at Week 12 vs C4 Week 12 Change from Baseline value
 
• Scatterplot of Bile Acid concentrations at Week 12 vs Bile Acid Week 12 Change from Baseline value
 
• Boxplot of predose concentration at Weeks 2, 4, 8, and 12 for EDP-305 and EP-022679 by treatment group for subjects with and without pruritus
 
• Listing of EDP-305 & EP-022679 concentrations for subjects with pruritus
 

8.9	Subgroup Analyses: All
8.10.2	Interim Analysis #2: All
8.11	Analysis of COVID-19 Impact on Study: All

- The following listings have been added: Informed Consent and Rescreening data will be listed for all enrolled subjects.
- Inclusion and exclusion criteria will be listed for all enrolled subjects.

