### SAS code for MMRM analysis

```
PROC MIXED data = dataset method=type3;  
  class trt01pn(ref=0) visitn usubjid ;  
  model CHG = trt01pn visitn trt01pn*visitn baseline_NAS baseline_parameter  
  /ddfm=KR;  
  repeated trt01pn / type = UN subject = usubjid;  
  lsmeans trt01pn*avisitn /pdiff ;  
  ods output    LSMEANS=lsm  
                DIFFS=diff  
RUN;
```

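### The itch VAS model is specified with one covariance matrix for all arms, although itch variance is expected to rise with dose; if it does, the 1.5 mg versus placebo interval is roughly 10–20% too wide

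*Protocol*

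**What the plan says.** Protocol 11.6.1 allows an MMRM for repeated continuous endpoints and says of its error model: "An unstructured variance-covariance structure will be considered to model the within-patient error". The fallback is a heterogeneous Toeplitz structure, and degrees of freedom are Kenward-Roger. SAP 8.6.1 repeats this. SAP 8.6.3.2.1 makes it firm for itch: "Change from baseline for VAS and 5D-itch scale will be analyzed using a restricted maximum likelihood-based mixed model repeated measures (MMRM) technique". For the error model it only points back: "Variance-covariance structure to be used to model the within-patient error and results to be presented are described in" Section 8.6.1. The promised output is inferential: "The model will provide least-squares means (using type III sum-of-squares), standard errors, p-value and 2-sided 95% confidence interval for treatment differences for each visit".

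Neither text lets the matrix vary by treatment arm or calls for a sandwich variance. Heterogeneous Toeplitz lets the variance differ between visits, not between arms, and Kenward-Roger does not address unequal arms. As written, then, the text describes one matrix shared by placebo, 1.5 mg and 2 mg.

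The sample MMRM code in SAP Appendix A does not code that model. It reads "repeated trt01pn / type = UN subject = usubjid", so the matrix is indexed by treatment, which is constant within a subject, instead of by visit. It also requests method=type3 where the text says restricted maximum likelihood.

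SAP Section 9 removes the histology, subgroup and second interim analyses after termination, but not the itch model. For analyses planned through Week 72, "only summary statistics will be provided post Week 12 visit". Modelled itch results therefore remain through Week 12.

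**The concern.** Protocol 8.3.5 treats a VAS above zero as itch, so a subject without itch scores zero. In such a score the variance depends mainly on the share of subjects who itch. In the earlier 12-week study (Protocol 1.4.2), "pruritus was present in approximately 51% of the subjects in the 2.5 mg arm compared to less than 10% in the 1 mg arm", with under 5% on placebo. Protocol 4.2.2 says that pruritus increases with exposure and expects rates of up to 25% at this trial's doses. Equal VAS variance in the three arms is thus not what the sponsor's own evidence suggests.

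With three arms, equal allocation does not protect a pairwise contrast, because the pooled variance also includes the arm that is not being compared. A high-variance 2 mg arm inflates the error for 1.5 mg versus placebo, and a low-variance placebo arm deflates it for 2 mg versus 1.5 mg.

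Pruritus is a secondary objective, helped to determine the doses and led 20.8% of the 2.5 mg arm to stop treatment in the earlier study. At stake is an itch increase at the lower dose that appears less certain than the data make it.

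**Working it through.** The plan gives no itch-score SD, effect size or interval width, so there is no stated figure to reproduce.

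**Inputs from the documents.** Itch rates in the earlier study are as above. Expected rates for the current doses are at most 25%, with a suggestion of at or below 19% (Protocol 4.2.2; 19% is the placebo rate of another FXR-agonist trial). The plan has 112 subjects per arm (Protocol 5.6). On the level of testing: "Inferential testing will be conducted using a 2-sided alpha of 0.05, unless stated otherwise".

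**Assumptions.** VAS is 0 with probability 1−p. Otherwise it is positive with coefficient of variation cv = 0.4, for example mean 5 and SD 2. Changing cv to 0.3 or 0.6 moves the ratios for 1.5 mg versus placebo by about 0.01.

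**Step 1, variance by arm**, in units of the squared mean itch score: V = p(cv² + 1 − p) = p(1.16 − p).
- 5%: 0.05 × 1.11 = 0.0555
- 10%: 0.10 × 1.06 = 0.1060
- 15%: 0.15 × 1.01 = 0.1515
- 19%: 0.19 × 0.97 = 0.1843
- 25%: 0.25 × 0.91 = 0.2275

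**Step 2, pooled against true error.** With complete data, a treatment-by-visit model with one unstructured matrix gives SE² = 2·Vpool/n at each visit, where Vpool is the mean of the three arm variances. The true value is (Va + Vb)/n. The width ratio is √[2·Vpool/(Va + Vb)], which does not depend on n. Coverage is 2Φ(1.96 × ratio) − 1.

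Example, 5/15/25% (placebo/1.5 mg/2 mg): Vpool = (0.0555 + 0.1515 + 0.2275)/3 = 0.1448. For 1.5 mg versus placebo the ratio is √(0.2897/0.2070) = 1.18. For 2 mg versus 1.5 mg it is √(0.2897/0.3790) = 0.87.

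| Itch %, placebo/1.5/2 mg | 1.5 mg vs placebo | 2 mg vs placebo | 2 mg vs 1.5 mg |
|---|---|---|---|
| 5/10/19 | 1.20 (98.1%) | 0.98 (94.5%) | 0.89 (91.9%) |
| 5/15/25 | 1.18 (98.0%) | 1.01 (95.3%) | 0.87 (91.3%) |
| 5/19/25 | 1.14 (97.5%) | 1.05 (96.0%) | 0.87 (91.2%) |
| 5/25/25 | 1.10 (96.8%) | 1.10 (96.8%) | 0.87 (91.0%) |
| 5/10/10 (corner) | 1.05 (96.1%) | 1.05 (96.1%) | 0.92 (92.8%) |
| 5/10/25 (corner) | 1.27 (98.7%) | 0.96 (93.9%) | 0.88 (91.6%) |
| 19/25/25 | 1.02 (95.4%) | 1.02 (95.4%) | 0.97 (94.2%) |
| 19/19/19 | 1.00 (95.0%) | 1.00 (95.0%) | 1.00 (95.0%) |
| 5/25/10 (order reversed) | 0.96 (93.9%) | 1.27 (98.7%) | 0.88 (91.6%) |

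**Step 3, the condition for each direction.** 1.5 mg versus placebo is too wide when V(2 mg) exceeds the mean of V(1.5 mg) and V(placebo). 2 mg versus 1.5 mg is too narrow when V(placebo) is below the mean of the two active variances.

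**Step 4, simulation.** Zero-inflated gamma scores (cv 0.5, 112 per arm, 5/15/25%) gave pooled coverage of 98.2%, 95.2% and 91.4% for the three contrasts. Arm-specific variances gave 94.7–94.9%. A five-visit likelihood fit with itch-driven dropout gave the same ratios, 1.18 and 0.87.

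**Step 5, power, for illustration at 112 per arm.** With mean 5 and SD 2, the variances are 1.39, 3.79 and 5.69 (pooled 3.62), and the 1.5 mg versus placebo difference is 5 × (0.15 − 0.05) = 0.5. The true SE is √(5.175/112) = 0.215 and the pooled SE is √(2 × 3.62/112) = 0.254. Power is Φ(0.5/0.215 − 1.96) = 64% with the correct SE. With the pooled SE it is Φ((0.5 − 1.96 × 0.254)/0.215) = 50%.

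**Step 6, background variance.** If itch unrelated to drug adds a variance of 1 to 3 in every arm, the ratios shrink to 1.14–1.09 and 0.90–0.93.

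**The case against.** The strongest reply is that unequal variance is inferred, not documented. The earlier rates are pruritus incidence over 12 weeks at 1 mg and 2.5 mg, not VAS at a visit at 1.5 or 2 mg. VAS records the worst itch of the past two weeks, so subjects with no pruritus event may score above zero, and the modelled endpoint is change adjusted for baseline. All of this stands, and it makes the point conditional. A reader might infer that the intervals are simply wrong; the documents do not support that. With placebo itch near 19% the error is 2–3% or nothing, and if itch fell from 1.5 to 2 mg the first direction would reverse.

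A reader might also infer that Appendix A codes the pooled matrix, so that every reported standard error uses it. It does not: its repeated effect is treatment. The pooled matrix comes from the text, and code and text disagree.

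The practical effect is limited. 2 mg versus placebo is little affected in most cases. The 1.5 mg versus placebo interval errs on the conservative side. The only contrast that is clearly too narrow, dose against dose, is a by-product: the Protocol synopsis disclaims formal comparison of dose levels in its safety analyses. Pruritus is also captured as adverse events and in by-visit, by-arm summaries that include the SD, where unequal spread would show. These points stand. They reduce the weight of the issue but do not justify a pooled standard error in the itch model itself.

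The argument does not carry over to 5D-itch without more information. Under Protocol 8.3.5 that scale follows only a VAS above zero, while a schedule footnote says that up to two scales are used for every subject. If subjects without itch have no 5D score, there is no mass of non-itchers at one value.

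**Conclusion.** The point holds for VAS, conditionally. The text specifies one covariance matrix for all arms, and the sponsor's dose-dependent itch rates make equal variances unlikely. If placebo itch is about 5% and itch on 1.5 and 2 mg is 10–25% and does not fall with dose, the 1.5 mg versus placebo interval is about 10–20% too wide in the central cases (coverage 97–98%). The corners of that range give 5% and 27%. The incidental dose-against-dose interval is about 11–14% too narrow (coverage 91–92%; 8% at the mildest corner). 2 mg versus placebo is within about 5%, rising to about 10% too wide when both doses itch at 25%.

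This rests on an assumed zero-inflated score, since no itch SD is given. The tabulated ratios also assume complete data and no baseline adjustment. The power loss from 64% to 50% is illustrative only: the trial stopped early, and the documents do not say how many subjects reached Week 12. This is a moderate, inexpensive improvement to a secondary analysis and does not threaten the trial's conclusions.

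**What to change.** For VAS, in SAP 8.6.3.2.1 as a stated exception to 8.6.1, and in Appendix A:

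- Correct the MMRM code so that visit is the repeated effect, and reconcile its estimation method with the restricted maximum likelihood named in the text.
- Estimate the covariance by arm (type=UN, subject=usubjid, group=treatment).
- If that does not converge, or an arm has almost no itch at a visit, keep the common unstructured matrix and report empirical (sandwich) standard errors. Name the degrees-of-freedom method that then replaces Kenward-Roger. A common Toeplitz matrix would not help.
- Apply the same to 5D-itch only if subjects with VAS = 0 receive a 5D score, and say which of the two Protocol statements governs.

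If treatment codes are already open, report this as a labelled sensitivity analysis and justify it in the study report; Protocol 11.1 allows SAP changes only before unblinding.

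Cost: SAP wording and one code option, in code that needs correcting anyway. Five post-baseline assessments to Week 12 (Day 7, Weeks 2, 4, 8 and 12) need 5 × 6/2 = 15 covariance parameters per matrix, so 45 instead of 15. Small arms are the weak spot. At 5% itch and 30 subjects, the chance that no placebo subject itches at a given visit is 0.95³⁰ = 21%. By-arm coverage in arms of about 25–40 is then about 92–95%. The sandwich fallback depends on the same few placebo subjects with itch, so it eases this problem without removing it.

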### **11.7.2. Adverse Events**

Adverse events will be summarized by the Medical Dictionary for Regulatory Activities (MedDRA) system organ class and preferred term by treatment group. All subjects in the safety analysis set will be included in the summaries. Treatment-Emergent are defined as reported AEs that first occurred or worsened during the postbaseline phase compared to baseline. The maximum severity at baseline will be used as baseline severity. If the maximum severity during postbaseline is greater than the maximum baseline severity, then event is considered Treatment-Emergent. No statistical testing will be performed.

Summaries of AEs will include the following at a minimum:

- An overall summary of AEs with a line for each of the categories provided below:
- TEAEs
- Related TEAEs
- Maximum Severity TEAEs
- Treatment-Emergent by Severity
- Treatment-emergent AEs leading to study drug discontinuation
- AEs leading to death
- SAEs
- Related Treatment-Emergent SAEs

### **11.7.3. Clinical Laboratory Data**

Laboratory assessments will be reported as mean change from baseline across scheduled visits, and as the incidence rate of shift change from baseline. Shift from baseline tables will be generated for each treatment group for selected analytes. Laboratory shifts will be displayed as

treatment-emergent abnormal, high, or low results. The following details the summary types where LLN = Lower limit of the normal range, ULN = Upper limit of the normal range.

For categorical tests: Treatment-emergent abnormal is defined as a change from normal at baseline to abnormal at any postbaseline visit

For continuous tests:

- Treatment-emergent high is defined as a change from a result less than or equal to the high limit at baseline to a value greater than the high limit at any time postbaseline.  
Results will be reported according to any value greater than the high limit, any value greater than 2x ULN and 3x ULN
- Treatment-emergent low is defined as a change from a result greater than or equal to the low limit at baseline to a value less than the low limit at any time postbaseline  
Results will be reported according to any value less than the lower limit, any value less than 2x LLN and 3x LLN.

#### **11.7.4. Electrocardiogram Data**

The QT interval has an inverse relationship with heart rate. The measured QT intervals will be corrected for heart rate in order to determine prolongation relative to baseline. The QT/QTc interval will be corrected based on Fridericia's correction:  $QTc = QT / (RR \text{ interval})^{1/3}$ , in seconds. The QT parameters will be summarized by observed and change from baseline over visits.

A categorical analysis of QT/QTc will be based on the number and percentage of subjects meeting or exceeding the following:

- Absolute QT/QTc interval prolongation
  - QTc interval > 450
  - QTc interval > 480
  - QTc interval > 500
- Change from Baseline in QTc interval
  - QTc interval increases from baseline >30
  - QTc interval increase from baseline >60.

#### **11.7.5. Vital Signs**

The incidence rate of subjects with treatment-emergent vital sign changes at any postbaseline visit will be summarized. Specific criteria for the classification of treatment-emergent will be documented in the SAP. Vital sign observed, change, and percent change will be summarized by treatment over visits.

#### **11.7.6. Concomitant Medications**

The number and percentage of subjects taking concomitant medications will be coded according to latest WHO ATC level 4 and WHO preferred term. Summaries will be provided by ATC level 4 and preferred term. Subjects in the safety population will be summarized by treatment group.

### **11.7.7. Physical Examinations**

Physical examination data will be provided in data listings.

